### **Comparison of preoperative and intraoperative imaging – evaluation of resection**

Matching of the preoperative MRI (that includes the preoperatively segmented resection margins) with the intraoperative CBCT images is performed using the above mentioned imaging software WorldMatch.

- For the patients included in the first phase of the study, after the acquisition of the CBCT scans, the maxillectomy is terminated and the reconstruction of the maxilla follows according to the standard procedure. Preoperative and intraoperative imaging matching will be performed postoperatively. The matching procedure is based on the bony structures surrounding the tumor area on MRI and CBCT. The tumor area shown in MRI is expected to be occupied by air in the post-operative CBCT. Figure 3 summarizes the procedure followed for phase I patients.
- For the patients of the second phase, thorough evaluation of the matched images is performed by the head and neck surgeon, before the reconstruction of the maxilla. If the excision is fully accomplished according to the preoperative plan, then the resection procedure is terminated and the reconstruction of the maxilla follows. The surgical procedure will be continued, only in case that there is suspicious residual tumour, included in the imaging resection planning. The complementary tissue resection is limited at the level where the residual tumour is detected, based on anatomical landmarks. After the supplementary resection, a second CBCT is obtained, as described in the previous section, and the same fusion procedure with the preoperative imaging is repeated. This second imaging evaluation is used to confirm the additional excision of the residual tumour. No more than two CBCT scans will be performed. The whole procedure for phase II patients is summarized in Figure 4.

[figure not shown]

Figure 3. Flowchart of work-up for patients in phase I.

[figure not shown]

Figure 4. Flowchart of work-up for patients in phase II.

Quality assessment of the preoperative and intraoperative imaging matching will be performed using two indices:

- The *Sorensen-Dice coefficient* is a statistic used for comparing the similarity of two images. Sørensen's original formula was intended to be applied to presence/absence data, and is:

$$QS = \frac{2[A \cap B]}{[A] + [B]}$$

A and B represent, in this case, two distinct images that are superimposed on one another (Figure 5). The index ranges between 0 and 1, depending on how complete is the overlap between the two images (0: no overlap; 1: complete overlap).

[figure not shown]

Figure 5. Two different images A and B, partially overlapping with each other.

- The *Hausdorff distance* is a metric between two point sets. It measures the extent to which each point of a set lies near some point of another set. Since an image can be considered as a set of points, Hausdorff distance can be used to determine the degree of resemblance of two images. The following formula is used to calculate the index, considering two different sets of points, A (including points  $a_1, a_2, a_3$  etc) and B (including points  $b_1, b_2, b_3$  etc):

$$H(A, B) = \max(h(A, B), h(B, A))$$

where

$$h(A, B) = \max_{a \in A} d(a, B) \text{ and } d(a, B) = \min_{b \in B} \rho(a, b)$$

$d(a, B)$  is the distance from a point  $a$  to the set  $B$ , and  $\rho(a, b)$  is a point distance in the metric space  $M$ .

Quality assessment of imaging matching will be performed after completion of the surgery.

#### 8.4 Withdrawal of individual subjects

Subjects can leave the study at any time, for any reason if they wish to do so without any consequences. The investigator can decide to withdraw a subject from the study for urgent medical reasons.

#### 8.5 Replacement of individual subjects after withdrawal

After withdrawal of a subject, the principal investigator will decide for their replacement.

#### 8.6 Follow-up of subjects withdrawn from treatment

Subjects that withdrew from the study will be followed up according to the normal, routine clinical procedures.

#### 8.7 Premature termination of the study

Not expected

## **9. SAFETY REPORTING**

### **9.1 Temporary halt for reasons of subject safety**

In accordance to section 10, subsection 4, of the WMO, the sponsor will suspend the study if there is sufficient ground that continuation of the study will jeopardise subject health or safety. The sponsor will notify the accredited METC without undue delay of a temporary halt including the reason for such an action. The study will be suspended pending a further positive decision by the accredited METC. The investigator will take care that all subjects are kept informed.

### **9.2 AEs and SAEs**

#### **9.2.1 Adverse events (AEs)**

Adverse events are defined as any undesirable experience occurring to a subject during the study, whether or not considered related to the investigational product / trial procedure/ the experimental intervention. All adverse events reported spontaneously by the subject or observed by the investigator or his staff will be recorded.

#### **9.2.2 Serious adverse events (SAEs)**

A serious adverse event is any untoward medical occurrence or effect that

- results in death;
- is life threatening (at the time of the event);
- requires hospitalisation or prolongation of existing inpatients' hospitalisation;
- results in persistent or significant disability or incapacity;
- is a congenital anomaly or birth defect; or
- any other important medical event that did not result in any of the outcomes listed above due to medical or surgical intervention but could have been based upon appropriate judgement by the investigator.

An elective hospital admission will not be considered as a serious adverse event.

The investigator will report all SAEs to the sponsor without undue delay after obtaining knowledge of the events. The sponsor will report the SAEs through the web portal *ToetsingOnline* to the accredited METC that approved the protocol, within 7 days of first knowledge for SAEs that result in death or are life threatening followed by a period of maximum of 8 days to complete the initial preliminary report. All other SAEs will be reported within a period of maximum 15 days after the sponsor has first knowledge of the serious adverse events.

### **9.2.3 Suspected unexpected serious adverse reactions (SUSARs)**

Not applicable

### **9.3 Annual safety report**

Not applicable

### **9.4 Follow-up of adverse events**

All AEs will be followed until they have abated, or until a stable situation has been reached.

Depending on the event, follow up may require additional tests or medical procedures as indicated, and/or referral to the general physician or a medical specialist.

SAEs need to be reported till end of study within the Netherlands, as defined in the protocol.

### **9.5 Data Safety Monitoring Board (DSMB)**

Not applicable

## **10. STATISTICAL ANALYSIS**

### **10.1 Primary study parameter(s)**

The primary study parameter is to evaluate the feasibility of utilizing CBCT as an imaging tool for the intraoperative verification of the complete resection of maxillary malignant tumours. The mean time of the procedure, including imaging, will be calculated. Additionally, the residual tumour volume in the CBCT scans will be estimated, as well as the ratio to the planned resection volume in the preoperative MRI. Quality assessment of the CBCT and MRI matching will be performed using the "Sorensen-Dice coefficient" and the "Hausdorff distance". Since this is a pilot study, no correlation to clinicopathological parameters will be performed.

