## SUMMARY

**Rationale:** Maxillary malignant neoplasms constitute a group of tumours that present often at an advanced stage. Their surgical management can therefore be challenging, regarding also their proximity to significant structures like the orbit and the brain. Particularly, cases with extensive disease and recurrent tumours are often incompletely resected and local treatment failure is commonly observed, ranging from 30% to 50%, according to the literature.

**Objective:** The primary objective of this study is to assess the feasibility of utilizing intraoperative cone-beam CT (CBCT) to verify the intended excision margins of maxillary malignant tumours. CBCT images will be matched with a preoperative planning of the resection margins on the preoperative MRI. This study will be the first step before conducting a randomised control study that will evaluate the efficacy of CBCT verified resection.

**Study design:** Exploratory pilot study.

**Study population:** A total number of 6 patients, above 18 years old, with maxillary cancer suitable for management with open maxillectomy will be included. All patients will undergo a pre-operative MRI scan of the maxilla for the evaluation of the local extent of the tumour. In this MRI, the tumour volume that is intended to be resected will be segmented.

The patients will be studied in two distinct phases:

1. Three patients will undergo the standard maxillectomy and intra-operative control with CBCT, however without any further resection
2. Three patients that will undergo the maxillectomy and intra-operative CBCT and additional excision, in case that residual tumour is observed based on the preoperative MR resection planning.

**Main study parameters/endpoints:** The main parameter of this pilot study is the technical success of implementing CBCT during maxillectomy as an additional tool for the control of the resection. Operating time will be recorded and the mean duration of the procedure will be calculated. Assessment of the possible residual tumour volume will be also performed based on the intraoperative CBCT, as well as comparison to the planned resection volume as calculated in the preoperative imaging planning. The quality of CBCT and MRI scan matching will also be evaluated. No correlation to clinicopathological parameters will be established in this study.

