### **4.4 Sample size calculation**

As this is a pilot study, no power calculation on sample size has been performed. A total number of 6 patients is considered sufficient to be included, to observe and test the technical feasibility.

Preoperative imaging with MRI of the maxilla will be obtained for all patients. Segmentation of the resection area will be then performed on the coronal and transverse sections of the MRI scans of each patient using the imaging processing software WorldMatch. Two distinct phases, each one including 3 patients, will be further created:

- In the first phase, the patients will undergo the conventional open maxillectomy procedure and the intraoperative imaging with the CBCT. Comparison of the preoperative and intraoperative scans will be conducted, using imaging fusion of the MRI and the CBCT

scans. No further intervention will be applied to this group, independently of the result of the intraoperative imaging.

- In the second phase, the patients will also undergo the primary resection and the intraoperative imaging. However, if the comparison of the preoperative with the intraoperative imaging reveals residual tumour that is included in the preoperative imaging resection planning, then the surgical procedure will continue in order to excise the target tissue. In this case a second CBCT will be carried out to confirm the complete resection.

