## **5. TREATMENT OF SUBJECTS**

### **5.1 Investigational treatment**

All patients included in the study have disease that can be managed by open maxillectomy. In general, and depending on the extension of the tumour, different approaches can be used for an open maxillectomy. Common incisions include the lateral rhinotomy, the Weber-Ferguson incision or the modified Weber-Ferguson incision with a Lynch extension. The resection may include one of the following procedures:

- **Medial maxillectomy:** The extent of bone resection includes the inferior and middle turbinates and ethmoid air cells cephalad and to the floor of the nasal cavity caudad. It is indicated for well-differentiated or low-grade malignant tumours and other tumours of limited extent on the lateral wall of the nasal cavity or the medial wall of the maxillary antrum.
- **Peroral partial maxillectomy (Infrastructure Maxillectomy):** when the upper alveolar ridge or hard palate are involved.
- **Subtotal maxillectomy:** A subtotal maxillectomy essentially removes the entire maxilla except the floor of the orbit.
- **Total Maxillectomy:** Complete removal of the maxilla becomes necessary when a primary tumour arising from the surface lining of the maxillary sinus fills up the entire antrum. Primary mesenchymal tumours arising in the maxilla such as soft tissue and bone sarcomas also require total removal of the maxilla to encompass the entire lesion.
- **Total Maxillectomy with Orbital Exenteration:** A radical maxillectomy with orbital exenteration is indicated when a primary tumor of the nasal cavity or paranasal sinuses extends into the orbit through the orbital periosteum. Orbital exenteration of a functioning eye with normal vision is considered only if the possibility of a curative resection exists. Removal of a functioning eye for a palliative operation is not recommended.
- **Total Maxillectomy with Orbital Exenteration and Reconstruction with Free Tissue Transfer.**

After completion of the resection, intraoperative CBCT will be obtained. The patients included in the second phase of the study may receive further resection and a second CBCT scan to confirm that the intended treatment volume is resected.

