## 8.2 Randomisation, blinding and treatment allocation

There is no randomization or blinding.

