### **11.4 Benefits and risks assessment, group relatedness**

The burden and risk is minimal, whereas the benefits are evident, not only for (future) patients, but also in general.

Burden:

The burden for the individual patient is the extra operating time it takes due to additional imaging procedure (approximately 15 minutes for each CBCT scan).

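### Time is summarised only as the mean length of the whole procedure, so the time added by the CBCT workflow cannot be separated out

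*Protocol*

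**What the plan says.** Two places in the protocol define the time measure. Section 10.1 states "The mean time of the procedure, including imaging, will be calculated". The Summary, under main study parameters, states "Operating time will be recorded and the mean duration of the procedure will be calculated". Both refer to the procedure as a whole, and 10.1 includes the imaging in it.

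The protocol's only statement about added time is the burden estimate in section 11.4, repeated in the Summary: "approximately 15 minutes for each CBCT scan".

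The design around this measure is as follows.

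- Section 4.4: six patients, three per phase ("A total number of 6 patients is considered sufficient to be included, to observe and test the technical feasibility"). All of them have the intraoperative scan.
- Section 8.2: "There is no randomization or blinding". No group or historical series without CBCT is named.
- Section 5.1: "The resection may include one of the following procedures", followed by six types of resection. They run from medial maxillectomy to total maxillectomy with orbital exenteration and free tissue reconstruction.
- Section 8.3: in phase 1 there is one scan, and matching is done after surgery. In phase 2 matching and evaluation take place before reconstruction, and further resection, a second scan and a second matching may follow. Two scans is the maximum.

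Operating time does not appear among the four main endpoints in 8.1.1, and 8.1.2 lists no secondary parameters.

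**The concern.** A feasibility pilot of an intraoperative imaging step should be able to say what that step costs in theatre time. The planned statistic describes how long the operations took, imaging included, and the length of a maxillectomy depends mainly on what has to be resected and reconstructed. With every patient scanned and nothing timed separately, the reported mean mixes case mix, scanning, matching and re-resection.

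Two things are lost. The study's own data cannot inform its burden estimate of about 15 minutes per scan. The phase 2 workflow, in which CBCT actually guides the operation, has its extra time hidden most completely, because matching, evaluation and re-resection all fall inside the same total. Step times that are not noted during surgery may not be recoverable afterwards.

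There is also an inconsistency of listing: the Summary and 10.1 treat time as a parameter, while 8.1.1 omits it.

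**Working it through.** The protocol gives no figure to reproduce for this analysis: no expected duration, standard deviation or target. The check is whether the added time can be identified from what is reported.

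**1. Components of total time.** For patient i, write

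T_i = B_i + c·s_i + M_i + R_i

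- B_i: time of the operation apart from the study imaging workflow (varies with the six types in 5.1; not recorded separately).
- c: time per scan (about 15 minutes in 11.4).
- s_i: number of scans (1 in phase 1; 1 or 2 in phase 2; section 8.3).
- M_i: intraoperative matching and evaluation (zero in phase 1, where matching is postoperative).
- R_i: supplementary resection (zero in phase 1).

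Only the mean of T_i is planned.

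**2. Pooled mean.** With k phase 2 patients having a second scan (k = 0 to 3), there are 6 + k scans, and

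mean T = mean B + c(6 + k)/6 + (sum of M + sum of R)/6.

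Taking c = 15 minutes, the scan term is:

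| k | 15 × (6 + k)/6 |
|---|---|
| 0 | 15.0 min |
| 1 | 17.5 min |
| 2 | 20.0 min |
| 3 | 22.5 min |

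Matching and re-resection come on top. The count k will be known, but mean B will not. If c were larger by d minutes and each B_i smaller by d·s_i, every T_i would be unchanged. The same data therefore fit any c that leaves B_i plausible. This does not depend on the number of patients.

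**3. Means by phase.**

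- Phase 1: mean B1 + c.
- Phase 2: mean B2 + c(3 + k)/3 + mean M + mean R.
- Difference: (mean B2 − mean B1) + c·k/3 + mean M + mean R.

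The first scan cancels from the difference. At c = 15 the remaining scan term is 15 × k/3 = 0, 5, 10 or 15 minutes for k = 0, 1, 2, 3. It is still added to the matching and re-resection times and to any difference in case mix between two non-randomised groups of three. Splitting by phase therefore does not isolate the scan time either.

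**4. Direct timing.** Section 8.3 already describes usable time points: the surgeon calls for imaging, and after acquisition the C-arm goes back to its parked position. Timing that interval gives c directly for each of the 6 to 9 scans, with no comparator and without needing B_i.

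**The case against.** The strongest reply is that the protocol never asks how much time CBCT adds. Its objectives in section 2 concern verifying resection of the planned volume and the feasibility of segmentation. The endpoints in 8.1.1 are marking the volume, obtaining the scan, matching quality and rate of complete resection. Time is one descriptive sentence in 10.1, and the 15 minutes is a burden statement to patients, not a hypothesis. Component timings could also appear in a statistical analysis plan or on the data form.

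Much of this stands, and it limits the point. Four stronger readings are tempting and not supported:

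- **That the study fails a promised test of the 15 minutes.** No section promises one.
- **That a planning figure for the later randomised trial is lost.** The Summary and section 1 announce that trial but do not say that operating time from this pilot will be used to plan it.
- **That one mean over both phases is prescribed.** Pooling is the natural reading of 10.1 but is not stated. The conclusion does not need it, since phase-specific means fail too.
- **That the mean of six is too imprecise.** The protocol plans no interval or test of operating time, gives no standard deviation, and says "As this is a pilot study, no power calculation on sample size has been performed". Any half-width would rest on an assumed spread for something the plan does not report. The problem is identification, not precision.

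A reader might also cite "different approaches can be used for an open maxillectomy" for the case mix. In section 5.1 that phrase introduces the incisions; the range of resections comes from the list that follows.

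What the reply does not remove is that the protocol chose a time measure, put it under the main parameters in the Summary and under the primary parameter in 10.1, and defined it as total time. That is a stated statistic, not a detail left open.

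**Conclusion.** The point holds as a modest, inexpensive improvement. As written, the time analysis cannot show how much time the CBCT workflow adds, pooled or by phase, and so cannot inform the protocol's own estimate of about 15 minutes per scan. This follows from three features of the document: every patient is scanned, no time without CBCT is available, and no component is timed. It needs no assumption about variability. The 15.0 to 22.5 minutes shown for the scan share takes the protocol's 15 minutes as exact and is illustrative only.

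None of the four endpoints in 8.1.1 is undermined, and patient safety is not affected. The absence of time from 8.1.1 is a separate, minor inconsistency that the same edit can settle. A statistical analysis plan not seen here might add step timings, but the protocol text would still need to agree with it.

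**What to change.** In section 10.1, replace the single mean by component times recorded for each patient:

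- (a) for each scan, from the surgeon's request for imaging to the C-arm being parked;
- (b) in phase 2, the intraoperative matching and evaluation time, for each round;
- (c) any supplementary resection time.

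List all six patients by phase, with type of maxillectomy and number of scans, and summarise by median and range. Set (a) descriptively beside the 15-minute figure, without a test. Keep total operating time as background. Make the Summary agree, and add time as a parameter in 8.1.1 so that the three places match.

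The cost is a few extra time stamps on the data form and revised wording in three places. No change to sample size, treatment or imaging is involved. The stamps need to be in place before the first operation.

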## **10.2 Interim analysis**

Not applicable

## **11. ETHICAL CONSIDERATIONS**

### **11.1 Regulation statement**

This study will be conducted according to the principles of the Declaration of Helsinki (adopted during 59th WMA General Assembly, Seoul, October 2008) and in accordance with the Medical Research Involving Human Subjects Act (WMO) and other guidelines, regulations and Acts.

### **11.2 Recruitment and consent**

All patients will be informed by their head and neck surgeon about the aims of the study, the possible adverse events, the procedures and possible hazards to which the patient will be exposed. They will be informed as to the strict confidentiality of their patient data, but that their medical records may be reviewed for trial purposes by authorized individuals other than their treating physician. Patients are asked to fill in and sign an informed consent form and return this to the principal investigator if they agree to participate in this study. The informed consent procedure is according to the ICH Guidelines on Good Clinical Practice. An example of the translated informed consent form is enclosed in appendix 1.

This protocol will be submitted for approval by the Medical Ethics Committee of the NKI-AvL before the study starts and patients can be included.

### **11.3 Objection by minors or incapacitated subjects**

Not applicable

### **11.4 Benefits and risks assessment, group relatedness**

The burden and risk is minimal, whereas the benefits are evident, not only for (future) patients, but also in general.

Burden:

The burden for the individual patient is the extra operating time it takes due to additional imaging procedure (approximately 15 minutes for each CBCT scan).

